12.7 Interim analyses

No formal interim analysis is planned for this study. However, summaries of safety and PK data will be produced to support the regular safety monitoring conducted by the DMC and the confirmation of RP2D. Efficacy data may also be analyzed

when all patients (Phase I and Phase II) have completed 24 weeks (approximately 6 months) of treatment or discontinued earlier. The final analysis will be conducted when all patients have completed Month 24 (i.e., the end of the long-term follow-up period), unless the patients discontinue earlier.

In this clinical trial it is not planned to test specific efficacy hypotheses but to provide estimates of efficacy endpoints for the pediatric study population and therefore no-alpha adjustment will be made for earlier estimates of efficacy endpoints. However, the data for the primary efficacy assessment, ORR at Day 28 will already be final once all patients have completed 6 months of treatment.

12.8 Sample size calculation

12.8.1 Primary endpoint(s)

In Phase I, 5 patients will be enrolled to each age group with no minimum for Group 4. A minimum of 5 patients in Group 1 will also undergo extensive PK sampling during Phase II. Should one or more of the 5 patients not be evaluable for PK analysis, additional patients may be enrolled to ensure a minimum of 5 evaluable PK profiles for Groups 1, 2 and 3.

A comparison of PK parameters (Cmax) from 5 pediatric patients (in Groups 2 and 3 separately) to ~25 adult patients (from study [\[\[CINC424C2301\]\]](#)) will be performed. With expected similarity in the point estimates across groups (geo-mean ratio, GMR = 1), and accounting for expected higher variability in the pediatric patients (CV% ~55.7%, [\(Loh et al 2015](#), detailed data on file) compared to ~40% in adults), the confidence interval for a GMR of 1 would be [0.609;1.641] which demonstrates clinically relevant comparability of exposure to adult exposure (within 2-fold).

Therefore, with a minimum of 5 evaluable profiles in each of Groups 2 and 3, combined with 5 evaluable profiles from Group 1 and further sparse PK samples in the Phase II of the study, there is sufficient precision to support the PK objectives of the study.

Should the exposure in Group 2, 3 or 4 not be confirmed following the PK sampling in at least 5 patients, additional patients will be enrolled in that specific age group until the dose/exposure is confirmed (i.e., selection of the RP2D for those ages based on exposure and safety review by the DMC). Once the RP2D is selected for Groups 2 and 3 any further eligible patients between the ages of 2 years and 12 years will be enrolled into the Phase II, and Group 4 will begin enrolling patients in the Phase I.

Although several studies of treatments for aGvHD and SR-aGvHD have included pediatric patients, it is difficult to find recent estimates for steroid response in de novo aGvHD pediatric patients or BAT response in SR-aGvHD pediatric patients. A review of 443 patients (including 175 patients < 20 years), reported a CR/PR rate of 55% at Day 28, no association with ORR rate and patient age was found ([MacMillan et al 2010](#)). Other papers report response rates in the ranges 50-60% for de novo and SR-aGvHD ([Martin et al 2012](#)).

The sample size for the Phase II objective of measuring ORR at D28 is 45 patients regardless of age. Of these there must be at least 20% of the patients with treatment naïve aGvHD and 40% of the patients with SR-aGvHD to ensure the sample is representative of the study population. The remaining can be filled with either diagnosis. Any patient receiving the confirmed RP2D during the Phase I will be counted towards the 45 patients.

The sample size calculation for the Ph II activity objective is based on the ORR at Day 28. Assuming the true ORR at Day 28 of the study population is 80%, an overall sample size of 45 patients would have 90% probability to have a 90% CI for ORR with lower limit $\geq 60\%$. In addition, considering the Saw-Toothed behavior of power waving for single binomial proportion using an exact method ([Chernick and Liu 2002](#)) a minimum sample size of 45 subjects would provide $>85\%$ probability to have a 90% CI with lower limit $\geq 60\%$. [Chernick and Liu 2002 Table 12-2](#) provides estimates of the probability to have a 90% CI with lower limit $\geq 60\%$, minimum number of responders required to have a 90% CI with lower limit of $\geq 60\%$ and two-sided 90% Clopper-Pearson CIs for various sample sizes. Patients treated at the RP2D from the Phase I contribute to this analysis.

Table 12-2 Probability to have a 90% CI with lower limit $\geq 60\%$ and 90% confidence intervals for different number of patients

Sample size	Minimum No. of responders	Response Rate	Probability to have a 90% CI with lower limit $\geq 60\%$	90% CI
37	28	0.76	0.809	0.614 0.867
38	29	0.76	0.784	0.623 0.871
39	29	0.74	0.859	0.604 0.854
40	30	0.75	0.839	0.613 0.858
41	31	0.76	0.818	0.621 0.861
42	31	0.74	0.882	0.604 0.846
43	32	0.74	0.864	0.612 0.849
44	33	0.75	0.846	0.620 0.853
45	33	0.73	0.901	0.604 0.838
46	34	0.74	0.886	0.612 0.842
47	35	0.74	0.869	0.619 0.846
48	35	0.73	0.916	0.604 0.832
49	36	0.73	0.903	0.612 0.835
50	37	0.74	0.889	0.619 0.838

13 Ethical considerations and administrative procedures

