3.1.1 Determination of recommended Phase II dose

- Group 2 (age ≥6y to <12y) and Group 3 (age ≥2y to <6y): Physiologically based pharmacokinetic (PBPK) modeling will be used to derive a starting dosing for these patients, which is predicted to yield an exposure equivalent to that of a 10 mg BID in adults. The PBPK model will incorporate PK data from adult and adolescent patients with SR-aGvHD treated on study [CINC424C2301], and these predictions will be compared to existing data in pediatric patients from other indications (Loh et al 2015). The starting doses are thereby assigned as 5 mg BID (Group 2) and 4 mg/m² BID (Group 3).
- Group 4 (≥ 28 days to < 2 y): the absence of existing ruxolitinib PK data in this age group warrants a conservative approach. Therefore, the starting dose for Group 4 will be determined by using PK data generated in Groups 1, 2 and 3 (Table 3-1 and Table 3-2). These data will be used to inform the PBPK model in order to enable accurate predictions for these very young patients.

Groups 2 and 3 will enroll a minimum of 5 patients each. Full ruxolitinib concentration-time courses, safety and activity data will be collected over 28 days. Should one or more of the 5 patients not be evaluable, or until the dose/exposure is confirmed, additional patients may be enrolled to ensure a minimum of 5 evaluable patients per age group. This information will be used to assess the adequacy of this preliminary dose, which can be adapted if needed (e.g. to account for any potential difference between the expected and the observed ruxolitinib exposure).

If the exposure from the first 5 patients does not approximate the exposure of 10mg BID in adult and adolescent patients based on AUC and Cmax, at least an additional group of 5 patients will be enrolled in that specific age group. This second group of at least 5 patients may be administered a different starting dose to again target the 10mg BID adult exposure. This process will continue until the dose-exposure relationship is confirmed (i.e. selection of the RP2D for those ages based on exposure and safety review by the DMC). If the selected RP2D is higher than the starting dose assigned to the previous group of patients, intra-patient dose escalation is allowed ([Section 6.5.1.1](#)). Inversely, if the selected RP2D is lower than the starting dose assigned to the previous group of patients, intra-patient dose de-escalation is allowed.

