6.5 Dose escalation and dose modification

6.5.1 Dose escalation guidelines

Group 2 (age ≥ 6 y to < 12 y) and Group 3 (age ≥ 2 y to < 6 y): PBPK modeling will be used to derive a starting dosing for these patients, which is predicted to yield an exposure equivalent to that of a 10 mg BID in adults. The PBPK model will incorporate PK data from adult and adolescent patients with SR-aGvHD treated on study [\[CINC424C2301\]](#), and these predictions will be compared to existing data in pediatric patients from other indications ([Loh et al 2015](#)). The starting doses are thereby assigned as 5 mg BID (Group 2) and 4 mg/m² BID (Group 3).

Group 4 (≥ 28 days to < 2 y): the absence of existing ruxolitinib PK data in this age group warrants a conservative approach. Therefore, the starting dose for Group 4 will be determined by using PK data generated in Groups 1, 2 and 3 ([Table 3-1](#)). These data will enhance the PBPK model in order to better predict PK in patients below 2 years of age.

Groups 2 and 3 will enroll a minimum of 5 patients each. Full ruxolitinib concentration-time courses, safety and activity data will be collected over 28 days. Should one or more of the 5 patients not be evaluable, additional patients may be enrolled to ensure a minimum of 5 evaluable patients per age group. This information will be used to assess the adequacy of this preliminary dose, which can be adapted if needed (e.g. to account for any potential difference between the expected and the observed ruxolitinib exposure).

If the exposure from a minimum of 5 patients does not approximate the exposure of 10mg BID in adult and adolescent patients based on AUC and Cmax, an additional group of 5 patients will be enrolled in that specific age group. This second group of 5 patients will be administered a different starting dose to again target the 10mg BID adult exposure. This process will continue until the dose-exposure relationship is confirmed (i.e. selection of the RP2D for those ages based on exposure and safety review by the DMC). If the selected RP2D is higher than the starting dose assigned to the previous group of patients, intra-patient dose escalation is allowed ([Section 6.5.1.1.1](#)).

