3.5.2 Statistical hypothesis, model, and method of analysis

Pharmacokinetic parameters for patients in Groups 1, 2, 3 and 4 (who are part of the PAS) will be compared to adult information from study [\[CINC424C2301\]](#) through the use of ANOVA methods. The geometric mean ratio with 90% CI will be provided.

The response rates for ORR at Day 28 will be estimated on the Efficacy Evaluable Set (EES). Two-sided 90% confidence intervals [\[Clopper and Pearson 1934\]](#) will be calculated based on the exact method for binomial distribution. Summary statistics (frequencies and percentages) will be provided.

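### With five children per age group, the 90% CI for Cmax lies within 2-fold of adults only about 58% of the time at a true ratio of 1, so the quoted interval shows expected width, not comparability

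*Protocol*

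**What the plan says.** Protocol 12.8.1 sizes the Phase I PK comparison, and SAP section 4 repeats the text. The plan is "A comparison of PK parameters (Cmax) from 5 pediatric patients (in Groups 2 and 3 separately) to ~25 adult patients" from study CINC424C2301. The calculation is made "With expected similarity in the point estimates across groups (geo-mean ratio, GMR = 1", and "accounting for expected higher variability in the pediatric patients (CV% ~55.7", against about 40% in adults. It yields a single interval, which "would be [0.609;1.641] which demonstrates clinically relevant comparability of exposure to adult exposure (within 2-fold". The following paragraph counts five profiles in each of Groups 2 and 3, five from Group 1 and the sparse Phase II samples, and concludes that "there is sufficient precision to support the PK objectives of the study". Neither a confidence level, a variance method nor a probability is attached to the interval.

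The analysis is described in Protocol 12.4.2 and SAP 3.5.2 as a comparison with adults by ANOVA methods: "The geometric mean ratio with 90% CI will be provided". No bound is set there.

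The exposure rule stands apart from this. Protocol 3.1.1 brings in at least five more patients if the exposure of the first five "does not approximate the exposure of 10mg BID in adult and adolescent patients based on AUC and Cmax". The RP2D is then selected on exposure and safety review by the DMC. The texts differ on what the second group receives. Protocol 3.1.1 allows a different starting dose, whereas Protocol 6.5.1 says: "This second group of 5 patients will be administered a different starting dose to again target the 10mg BID adult exposure". SAP 2.1.1 is also worded as mandatory.

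**The concern.** An interval drawn around an assumed estimate of 1 tells the reader how wide the result is likely to be. It does not show that exposures are comparable, because the observed ratio from five children will rarely equal 1 and the observed width will vary too. The design property of interest is how often the CI will sit inside the 2-fold bound, and the documents do not give it.

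PK and the choice of RP2D are the Phase I primary objective, and this interval is the only numerical support for five profiles per group. A reader told that five profiles demonstrate 2-fold comparability will overrate what the Phase I comparison can show by itself. The same section already does the equivalent calculation for ORR. Protocol Table 12-2 gives the probability that the 90% CI clears 60% (0.901 at 45 patients, if the true ORR is 80%).

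**Working it through.** **Inputs.** From Protocol 12.8.1 and SAP 4: 5 children per group, about 25 adults, CV 55.7% and 40%, and a 2-fold bound, taken as 0.5 to 2.0 (±0.693 on the log scale). From Protocol 12.4.2 and SAP 3.5.2: a 90% CI.

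**Step 1: reproduce the stated interval.** Assume lognormal data and unequal variances (Welch).
- Log-scale variances: ln(1 + 0.557²) = 0.270 for children; ln(1 + 0.40²) = 0.148 for adults.
- SE of the log GMR: √(0.270/5 + 0.148/25) = 0.2449.
- Satterthwaite df: 4.92, so t(0.95) = 2.023.
- Half-width: 2.023 × 0.2449 = 0.495, and exp(±0.495) = 0.609 to 1.641.

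This matches exactly. A pooled-variance t interval on 28 df would be 0.712 to 1.404, and a 95% Welch interval 0.531 to 1.883, so neither is what was used. A t interval on 4 df that uses only the children's variance also rounds to 0.609 to 1.641.

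**Step 2: chance of lying within 2-fold, with the width held at the stated value.** The upper limit stays below 2 only if the observed GMR is below 2/1.641 = 1.219; the lower limit requires it to be above 1/1.219 = 0.82. At a true GMR of 1, P(|Z| < ln 1.219 / 0.2449) = P(|Z| < 0.81) = 0.58.

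**Step 3: let the sample variances vary too.** Simulating the log ratio and both sample variances (1 to 2 million draws) gives the probability that the 90% Welch CI lies wholly within 0.5 to 2.0:

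| True GMR | Children per group | Probability |
|---|---|---|
| 1 | 5 | 0.584 |
| 1, Groups 2 and 3 both, same adults | 5 each | 0.34 |
| 1.25 | 5 | 0.46 |
| 1 | 6 | 0.72 |
| 1 | 7 | 0.82 |
| 1 | 8 | 0.88 |
| 1 | 10 | 0.95 |

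**Step 4: sensitivity to method, n = 5, true GMR 1.**
- Children-only t on 4 df: 60%.
- CV used directly as the log SD, Welch: 51%.
- Variances treated as known (z): 76%.
- Pooled variance on 28 df: 85%, but with these unequal CVs the nominal 90% interval covers only about 82%.

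All figures are for Cmax. The exposure rule also looks at AUC, and the probability that both fit cannot exceed that for Cmax alone.

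**The case against.** The sponsor's best answer is that the sentence is conditional: it gives the interval for a GMR of 1 and promises no success rate. That is true, and it is why the interval itself is not in error. But the text goes on to say that the interval demonstrates comparability, which a conditional width cannot do.

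A second answer is that the analysis sections name ANOVA without specifying the variance, and a pooled version fits within 2-fold about 85% of the time. That also stands as a fact, so 58% should not be quoted without its method. Pooling, however, does not give the interval printed in 12.8.1, and it under-covers at the CVs printed there.

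Third, five is a minimum. Further children can be enrolled, and the probability rises quickly with each one. The statement being justified is nevertheless the one for five.

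Fourth, the precision sentence also counts Group 1 and the sparse samples, and a population PK analysis of pooled data is already planned. This softens the point. It does not rescue the comparability claim, which is built on 5 against 25 alone.

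Last, Amendment 3 reports enrolment complete, with 45 patients in Groups 1 to 3. The correction therefore bears on how the precision is described and reported, not on recruitment.

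**Conclusion.** The sample-size statement credits the design with a property that it does not reliably have. The stated interval is arithmetically right. Under the method that reproduces it, a perfectly matched Cmax gives a 90% CI inside 2-fold about 58% of the time per group and 34% for both groups, and 46% per group at a true GMR of 1.25. This rests on lognormal data, the documents' CVs, exactly five children per group and unequal variances.

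Three stronger readings are tempting and are not supported.
- A reader might infer that in the other 42% of cases the next five children would get a different dose. No section makes a CI beyond 2-fold the trigger. The rule is whether exposure approximates that of adults and adolescents on AUC and Cmax, with DMC review. If that were judged on the point estimate, it would lie within 2-fold in over 99% of trials at a true GMR of 1 (ln 2 / 0.2449 = 2.83 standard errors).
- A reader might infer that a CI including 1 will be taken as confirmation, so that real differences are missed. Neither document states such a rule.
- A reader might infer that SAP 3.5.2 needs a pass/fail criterion. The documents plan estimation, and a criterion added after enrolment was complete would be hard to defend.

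**What to change.** In Protocol 12.8.1 and SAP section 4:
- State that the interval is a two-sided 90% CI with unequal variances. If pooled ANOVA is mentioned, give its roughly 85% together with its roughly 82% coverage.
- Replace the claim that the interval demonstrates comparability with a description of it as the expected precision if the observed GMR is 1.
- Add the probability that the CI for Cmax lies within 2-fold at a true GMR of 1: about 58% per group and 34% for both groups at five profiles, about 82% per group at seven and 88% at eight.
- Qualify the sufficient-precision sentence: five profiles per group alone do not reliably show 2-fold comparability, and the conclusion also relies on the planned population PK analysis of all samples.

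In SAP 3.5.2, specify the same unequal-variance method for the GMR and its 90% CI. Separately, reconcile Protocol 3.1.1 with Protocol 6.5.1 and SAP 2.1.1 on whether the second group's different starting dose is optional or mandatory; no view is offered on which is right.

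The cost is wording in two documents and a less favourable stated precision. No extra patients are needed. Because enrolment is complete, the revised text should be marked as added after that point.

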13.1 Regulatory and ethical compliance

This clinical study was designed and shall be implemented, executed and reported in accordance with the ICH Harmonized Tripartite Guidelines for Good Clinical Practice, with applicable local regulations (including European Directive 2001/20/EC, US CFR 21), and with the ethical principles laid down in the Declaration of Helsinki.

13.2 Responsibilities of the investigator and IRB/IEC

Before initiating a trial, the investigator/institution must obtain approval/favorable opinion from the IRB/IEC for the trial protocol, written informed consent form, consent form updates, subject recruitment procedures (e.g., advertisements) and any other written information to be provided to subjects. Prior to study start, the investigator is required to sign a protocol signature page confirming his/her agreement to conduct the study in accordance with these documents and all of the instructions and procedures found in this protocol and to give access to all relevant data and records to Novartis monitors, auditors, Novartis Quality Assurance representatives, designated agents of Novartis, IRBs/IECs, and regulatory authorities as required. If an inspection of the clinical site is requested by a regulatory authority, the investigator must inform Novartis immediately that this request has been made.

13.3 Publication of study protocol and results

The protocol will be registered in a publicly accessible database such as clinicaltrials.gov and as required in EudraCT. In addition, after study completion and finalization of the clinical study report the results of this trial will be submitted for publication and posted in a publicly accessible database of clinical trial results, such as the Novartis clinical trial results website and all required Health Authority websites (e.g. Clinicaltrials.gov, EudraCT etc.).

For details on the Novartis publication policy including authorship criteria, please refer to the Novartis publication policy training materials that were provided to you at the trial investigator meetings.

13.4 Quality Control and Quality Assurance

Novartis maintains a robust Quality Management System (QMS) that includes all activities involved in quality assurance and quality control, to ensure compliance with written Standard Operating Procedures as well as applicable global/local GCP regulations and ICH Guidelines.

Audits of investigator sites, vendors, and Novartis systems are performed by auditors, independent from those involved in conducting, monitoring or performing quality control of the clinical trial. The clinical audit process uses a knowledge/risk based approach.

Audits are conducted to assess GCP compliance with global and local regulatory requirements, protocols and internal SOPs, and are performed according to written Novartis processes.

14 Protocol adherence

Investigators ascertain they will apply due diligence to avoid protocol deviations. Under no circumstances should the investigator contact Novartis or its agents, if any, monitoring the study to request approval of a protocol deviation, as no authorized deviations are permitted. If the investigator feels a protocol deviation would improve the conduct of the study this must be considered a protocol amendment, and unless such an amendment is agreed upon by Novartis and approved by the IRB/IEC/REB it cannot be implemented. All significant protocol deviations will be recorded and reported in the CSR.

16.1 Appendix 1: Infection Severity Grading

Table 16-1 Severity grading table and recurrence interval definitions

Type of Infection/ Severity Grade	Grade 1	Grade 2	Grade 3
Bacterial infections	Bacterial focus NOS requiring no more than 14 days of therapy for treatment (e.g urinary tract infection)	Bacteremia (except CoNS) without severe sepsis ***	Bacteremia with deep organ involvement (e.g. with new or worsening pulmonary infiltrates; endocarditis)
	Coag Neg Staph (S. epi), Corynebacterium, or Propriionibacterium bacteremia	Bacterial focus with persistent signs, symptoms or persistent positive cultures requiring greater than 14 days of therapy	Severe sepsis with bacteremia.
	Cellulitis responding to initial therapy within 14 days	Cellulitis requiring a change in therapy d/t progression Localized or diffuse infections requiring incision with or without drain placement	Fasciitis requiring debridement
		Any pneumonia documented or presumed to be bacterial	Pneumonia requiring intubation
	C. Difficile toxin positive stool with diarrhea < 1L without abdominal pain (child < 20 mL/kg)	C. Difficile toxin positive stool with diarrhea > 1L (child > 20 mL/kg) or with abdominal pain	C. Difficile toxin positive stool with toxic dilatation or renal insufficiency with/without diarrhea
Fungal infections	Superficial candida infection (e.g. oral thrush, vaginal candidiasis)	Candida esophagitis (biopsy proven).	Fungemia including Candidemia
		Proven or probable fungal sinusitis confirmed radiologically without orbital, brain or bone involvement.	Proven or probable invasive fungal infections (e.g., Aspergillus, Mucor, Fusarium, Scedosporium).
Fungal infections (continued)			Disseminated infections (defined as multifocal pneumonia, presence of urinary or blood antigen, and/or CNS involvement) with Histoplasmosis, Blastomycosis, Coccidiomycosis, or Cryptococcus.

Type of Infection/ Severity Grade	Grade 1	Grade 2	Grade 3
Viral infections			Pneumocystis jiroveci pneumonia (regardless of PaO ₂ level)
	Mucous HSV infection		
	Dermatomal Zoster	VZV infection with 3 or more dermatomes	Severe VZV infection (coagulopathy or organ involvement)
	Asymptomatic CMV viremia untreated or a CMV viremia with viral load decline by at least 2/3 of the baseline value after 2 weeks of therapy	Clinically active CMV infection (e.g. symptoms, cytopenias) or CMV Viremia not decreasing by at least 2/3 of the baseline value after 2 weeks of therapy	CMV end-organ involvement (pneumonitis, enteritis, retinitis)
	EBV reactivation not treated with rituximab	EBV reactivation requiring institution of therapy with rituximab	EBV PTLD
	Adenoviral conjunctivitis asymptomatic viruria, asymptomatic stool shedding and viremia not requiring treatment	Adenoviral upper respiratory infection, viremia, or symptomatic viruria requiring treatment	Adenovirus with end-organ involvement (except conjunctivitis and upper respiratory tract)
	Asymptomatic HHV-6 viremia untreated or an HHV-6 viremia with a viral load decline by at least 0.5 log after 2 weeks of therapy	Clinically active HHV- 6 infection (e.g. symptoms, cytopenias) or HHV-6 viremia without viral load decline 0.5 log after 2 weeks of therapy	
	BK viremia or viruria with cystitis not requiring intervention	BK viremia or viruria with clinical consequence requiring prolonged therapy and/or surgical intervention	
		Enterocolitis with enteric viruses	
		Symptomatic upper tract respiratory virus	Lower tract respiratory viruses
Viral infections (continued)	Viremia (virus not otherwise specified) not requiring therapy	Any viremia (virus not otherwise specified) requiring therapy	Any viral encephalitis or meningitis
			CNS or other organ toxoplasmosis
Parasitic infections			Strongyloides hyperinfection
Nonmicrobiologically defined infections	Uncomplicated fever with negative cultures responding within 14 days		

Type of Infection/ Severity Grade	Grade 1	Grade 2	Grade 3
	Clinically documented infection not requiring inpatient management	Pneumonia or bronchopneumonia not requiring mechanical ventilation	Any acute pneumonia requiring mechanical ventilation
		Typhlitis	
			Severe sepsis*** without an identified organism

*Concomitant or multimicrobial infections are graded according to the grade of the infection with the higher grade of severity.

**Therapy includes both PO and IV formulations

***Severe Sepsis:

Adults:

Hypotension

- A systolic blood pressure of <90 mm Hg or a reduction of >40 mm hg from baseline in the absence of other causes for hypotension

Multiple Organ Dysfunction Syndrome

- 2 or more of the following: Renal failure requiring dialysis, respiratory failure requiring bipap or intubation, heart failure requiring pressors, liver failure

Pediatrics:

- Pediatric SIRS definition and suspected or proven infection and cardiovascular dysfunction or ARDS or TWO OR MORE other organ dysfunctions

Pediatric SIRS definition:

Two or more of the following, one of which must be abnormal temperature or leukocyte count

1. Core temperature >38.5C or < 36C

2. Tachycardia, otherwise unexplained persistent in absence of external stimulus, chronic drugs or painful stimuli. or bradycardia, in < 1 year old, otherwise unexplained persistent.

3. Tachypnea or mechanical ventilation for an acute process not related to underlying neuromuscular disease or general anesthesia

4. Leukocytosis or leukopenia for age (not secondary to chemotherapy) or >10% bands

Pediatric organ dysfunction criteria:

Cardiovascular: despite administration of fluid bolus >40 mL/kg in 1 hour:

- Hypotension <5th percentile for age
- Pressors at any dose
- Two of the following:
- Capillary refill > 5 secs
- Core to peripheral temperature gap > 3oC
- Urine output < 0.5 mL/kg/hr
- Unexplained metabolic acidosis (Base deficit > 5.0 mEq/L)
- Blood lactate > 2 x ULN

Respiratory:

- ARDS or
- Intubated or
- >50% FiO₂ to maintain SaO₂ > 92%

Neurological:

- Glasgow Coma Score < 11 or
- Acute change in mental status with a decrease in GSC >3 pts from abnormal baseline

Type of Infection/ Severity Grade	Grade 1	Grade 2	Grade 3
Renal:			
• Serum creatinine > 2 x ULN for age or 2-fold increase in baseline creatinine			
Hepatic:			
• Total bilirubin > 4 mg/dL or • ALT >2 x ULN for agea			

Table 16-2 Four age groups relevant to HCT

Age	Tachycardia (bpm)	Bradycardia (bpm)	Tachypnea (breaths/min)	Leukocytosis / Leukopenia (WBC)	Hypotension Systolic BP mmHg
1 mo to 1 yr	>180	<90	>34	>17.5 to <5.0	<100
2 yr to 5 yr	>140	NA	>22	>15.5 to <6.0	<94
6 yr to 12 yr	>130	NA	>18	>13.5 to <4.5	<105
13 yr to < 18 yr	>110	NA	>14	>11 to <4.5	<117

Disseminated Infections:

- 1.Two or more non-contiguous sites with the SAME organism
- 2.A disseminated infection can occur at any level of severity, but most will be grade 2 or 3.

Recurrence Intervals to Determine Whether an Infection is the Same or New:

- 3.CMV, HSV, EBV, HHV6: 2 months (< 60 days)
- 4.VZV, HZV: 2 weeks (< 14 days)
- 5.Bacterial, non-C. difficile: 1 week (< 7 days)
- 6.Bacterial, C. difficile: 1 month (< 30 days)
- 7.Yeast: 2 weeks (< 14 days)
- 8.Molds: 3 months (< 90 days)
- 9.Helicobacter: 1 year (< 365 days)
- 10.Adenovirus, Enterovirus, Influenza, RSV, Parainfluenza, Rhinovirus: 2 weeks (< 14 days)
- 11.Polyomavirus (BK virus): 2 months (< 60 days)

For infections coded as “Disseminated” per the Infection Form, any previous infection with the same organism but different site within the recurrence interval for that organism will be counted as part of the disseminated infection.

